Appendix B Treatment Related Impact Measure - Diabetes (TRIM-D)

The following questions are concerned with the **MEDICATION that you take for your diabetes**. If you take more than one medication for your diabetes, or take medication for other conditions, please consider only your MEDICATION when answering these questions.

Please circle the response that most closely represents how you have felt about your MEDICATION over the PAST TWO WEEKS. Please mark only one number for each question. Remember there are no right or wrong answers to these questions.

1. How satisfied or dissatisfied have you been with:	Not at all satisfied	A little satisfied	Somewhat satisfied	Very satisfied	Extremely satisfied
a. The ease and convenience of your medication.....	1	2	3	4	5
2. How convenient or inconvenient is it for you to:	Not at all convenient	A little convenient	Somewhat convenient	Very convenient	Extremely convenient
a. Carry your medication and supplies around with you.....	1	2	3	4	5
b. Store your medication.....	1	2	3	4	5
c. Take your medication at the right time...	1	2	3	4	5
d. Prepare your medication for use.....	1	2	3	4	5
e. Monitor your blood sugar as often as necessary.....	1	2	3	4	5
3. How often does taking your MEDICATION interfere or not interfere with your:	Never/ Almost never interferes	Rarely interferes	Sometimes interferes	Often interferes	Almost always/ Always interferes
a. Meal time planning.....	1	2	3	4	5
b. Social activities.....	1	2	3	4	5
4. How satisfied or dissatisfied are you with your MEDICATION'S ability to:	Not at all satisfied	A little satisfied	Somewhat satisfied	Very satisfied	Extremely satisfied
a. Help you control your diabetes.....	1	2	3	4	5
b. Help you avoid high blood sugar (hyperglycemia).....	1	2	3	4	5
c. Help you avoid low blood sugar (hypoglycemia).....	1	2	3	4	5
d. Help you manage your weight.....	1	2	3	4	5
e. Help you prevent feeling tired or a lack of energy.....	1	2	3	4	5

5. Because of your MEDICATION, how OFTEN:	Never/ Almost never	Rarely	Sometimes	Often	Almost always/ Always
a. Do you have to limit your daily activities	1	2	3	4	5
b. Do you accomplish less than you would like to.....	1	2	3	4	5
c. Do you feel tension in your relationships with friends or family.....	1	2	3	4	5
6. Thinking about your MEDICATION, how often do you:	Never/ Almost never	Rarely	Sometimes	Often	Almost always/ Always
a. Miss a dose.....	1	2	3	4	5
b. Delay or postpone taking your medication.....	1	2	3	4	5
c. Take your medication at a different time than prescribed.....	1	2	3	4	5
d. Feel embarrassed or awkward when taking your medication.....	1	2	3	4	5
e. Worry that you forgot to take/or missed your last dose of medication.....	1	2	3	4	5
7. When I take diabetes MEDICATION I feel:	Never/ Almost never	Rarely	Sometimes	Often	Almost always/ Always
a. Depressed.....	1	2	3	4	5
b. Worried that the medication is not helping to slow down or prevent complications from my diabetes.....	1	2	3	4	5
c. Nervous or anxious.....	1	2	3	4	5
d. Worried about my blood sugar control....	1	2	3	4	5
e. Unhealthy.....	1	2	3	4	5
f. Angry.....	1	2	3	4	5
g. Worried about side effects from my medication.....	1	2	3	4	5

Thank You!

Appendix C Recommendations on basic genitourinary hygiene, maintaining hydration, and recognizing diabetic ketoacidosis

Patients with T2D are at risk for developing genitourinary (GU) infections. The following guidelines should be communicated to females and uncircumcised males regarding GU infections. Patient communication cards will be printed with the following:

For females:

“The following advice may be useful in helping you to keep your bladder and urethra free from infection:

- Go to the toilet as soon as you feel the need to urinate, rather than holding it in
- Wipe from front to back after going to the toilet
- Practice good hygiene by washing your genitals every day, and before having sex
- Empty your bladder after having sex.”

For uncircumcised males:

“The following advice may be useful in helping you to keep the foreskin free from infection:

- Wash the end of your penis and foreskin with soap and water (do not let soap get in the opening)
- After your shower or bath, dry the end of your penis and foreskin properly and replace the foreskin
- Also, when you urinate, slide the foreskin back enough so that urine does not get on the foreskin-this helps to keep it clean.”

Maintaining hydration:

Sodium-glucose cotransporter type 2 inhibitors are associated with osmotic diuresis and volume depletion, which may lead to dizziness or hypotension, especially in the elderly. Before initiating study drug (at Screening, Run-in and Randomization) and during all on-site study visits thereafter, assess volume status in patients with renal impairment, the elderly, in patients with low SBP, or if receiving diuretics, angiotensin-converting-enzyme inhibitors, or angiotensin receptor blockers. All patients will be advised to maintain proper fluid intake and to consider increasing it if they sense greater thirst, more urine production, or if they feel dizzy or faint.

Patient communication cards will be printed with the following for patients with T2D:

“The following advice may be useful in helping you to maintain proper hydration and prevent dehydration:

- Dehydration is when your body loses too much fluid, frequently due to diarrhea or increased urination

- Consider increasing the amount of fluids you drink if:
 - You sense greater thirst than usual
 - You have a dry mouth or cracked lips
 - You have a fever
 - You have diarrhea or vomiting
 - You urinate more frequently or in larger amounts than usual
 - You get up in the middle of the night to urinate (more than usual)
 - You feel dizzy or light-headed
 - You exercise, or when it is hot outside.”

Recognizing diabetic ketoacidosis

Potential GI AEs occurring with sotagliflozin may mask presenting symptoms of DKA. Patients will be provided with the BHB meter and instructions for use at the start of the Run-in Phase at Visit 2 (Week -4). Patients will be instructed to measure their BHB levels by fingerstick if they experience any symptoms consistent with ketosis/ketoacidosis throughout the entire study period. Patients will be instructed on how to respond (seek help, hydrate, ingest carbohydrates, etc) if they present with potential ketoacidosis symptoms and the BHB value is abnormal (>0.6 mM/L).

Patient communication cards will be printed with the following:

“If you have any of these symptoms on the list, measure your glucose and BHB by fingerstick, and then contact your study site immediately for assistance with managing your diabetes:

- Inability to maintain oral intake
- Generalized weakness
- Abdominal (belly) pain
- Increased weight loss
- Fever
- Frequent urination, including at night
- Fruity-scented breath
- Confusion
- Acute illness
- Consistently elevated blood glucose
- Feeling very thirsty or drinking a lot
- Nausea or vomiting
- Having trouble thinking clearly or feeling tired.

It is possible to have DKA even if your blood glucose is not elevated. Regardless of your blood glucose level, if you have any of these symptoms on the list, then contact your study site regarding the need to be evaluated for possible DKA, which will include specific blood testing. If your study site is closed and your study doctor is not available, go to the nearest emergency room for evaluation.

If your blood BHB reading is >0.6 mM/L and you have symptoms of ketoacidosis, seek help, hydrate, ingest carbohydrates, etc, as described above.

If you are scheduled for a procedure or surgery that requires you to not take any food or liquids, please contact your study doctor for instructions on continuing study drug. In such cases your study doctor may advise you NOT to take your study drug from the day prior to the procedure or surgery until after the procedure or surgery is complete, and you are taking food and liquids as you normally do.”

Whenever AE data is collected or the patient reports DKA or intercurrent illness (including infections), generalized weakness, increased weight loss, GI symptoms including nausea, vomiting, or abdominal pain or other symptoms or signs that the Investigator believes may be consistent with DKA, then the site will determine if an assessment for DKA is appropriate. If laboratory testing confirms presence of metabolic acidosis, then the “Possible DKA” eCRF will be completed.

Appendix D Measurement of blood pressure and heart rate

Equipment

1. Blood pressure measurements will be taken by an automated BP monitor or a manual sphygmomanometer. Same equipment should be used throughout the study and should be calibrated as per manufacturer recommendation.
2. Bladder Length – Should nearly or completely encircle the patient’s arm. For many adults, the standard “adult” size bladder is not long enough and the “large” size bladder is recommended.
3. Bladder Width – Should be at least 40% of the bladder length.

Patient factors

Extraneous variables associated with the measurement of BP should be minimized. These include:

1. Food intake, caffeine-containing beverages, cigarette smoking, or strenuous exercise within 2 hours prior to measurement.
2. Full urinary bladder.
3. The patient should not be allowed to talk while BP is being measured.
4. The patient should be placed in the examination room and the cuff should be placed on the patient’s nondominant arm. The proper sized cuff should fit snugly with the lower edge 2 to 3 cm above the antecubital fossa.
5. The patient should be allowed to sit quietly in a comfortably warm place (temperature around 25°C or 77°F) for 5 minutes with the arm supported at heart level, preferably with the cuff in place and with no restrictive clothing on the arm. The patient should be encouraged not to tense his/her muscles.

Determination of the reference arm

At Visit 1 (Week -6), seated BP should be measured in both arms after 5-minute rest period, and then again after 1 minute in both arms in seated position. The arm with the highest SBP will be determined at this visit, and BP should be measured always in this same arm throughout the study.

Measurement technique

[figure not shown]
At Visit 1, immediately following arm selection, with the patient in the same position, an additional seated BP should be measured in the selected arm (at least 1 minute after last measurement).

At all other on-site visits, following the 5-minute rest period, 3 separate seated BPs should be measured in the selected arm with at least 1 minute between BP measurements and with the cuff fully deflated between measurements.

All 3 BPs will be recorded in the patient's eCRF. The mean of the 3 seated BPs will constitute the BP value for that visit.

[figure not shown]
Three seated heart rate measurements will be obtained. The mean of the 3 seated heart rate measurements will constitute the pulse rate value for that visit.

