9.1.2 Secondary efficacy endpoints

Continuous secondary efficacy endpoints for the sotagliflozin 400 mg dose:

- Change from Baseline to Week 18 in FPG
- Change from Baseline to Week 18 in BW
- Change from Baseline to Week 12 in SBP for patients with Baseline SBP \geq 130 mmHg
- Change from Baseline to Week 12 in SBP for all patients
- Change from Baseline to Week 52 in HbA1c
- Change from Baseline to Week 52 in BW

Continuous secondary efficacy endpoints for the sotagliflozin 200 mg dose:

- Change from Baseline to Week 18 in HbA1c
- Change from Baseline to Week 18 in BW
- Change from Baseline to Week 18 in FPG
- Change from Baseline to Week 12 in SBP for patients with Baseline SBP \geq 130 mmHg
- Change from Baseline to Week 52 in HbA1c
- Change from Baseline to Week 52 in BW

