9.2.1.5 Vital signs

A complete physical exam (including sitting BP and heart rate, temperature and respiratory rate) will be performed at Visit 1 (Screening) and Week 26 (Visit 13). Abbreviated physical exams (including sitting BP and heart rate) will be performed at all other on-site visits. The abbreviated physical exam should focus on cardiac and respiratory systems, as well as any areas important for assessment of AEs if necessary.

Three separate seated BPs and heart rate measurements should be taken with at least 1 minute between measurements following a 5-minute rest period, and prior to phlebotomy. Full details and directions for the measurement of BP are presented in [Appendix D](#).

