2.1.4.5 Vital signs variables

Vital signs include: heart rate (HR), systolic and diastolic blood pressure, temperature, and respiratory rate (see study flowchart in [Appendix D](#) for designated visits). They will be performed after the patient has been seated for at least 5 minutes. Blood pressure and HR will be assessed 3 times with at least 1 minute between each measurement following the 5-minute rest period. The mean of the 3 measurements will be analyzed for each vital sign variable (HR, SBP, and DBP).

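### Appendix D of the protocol gives two incompatible rules for which arm to use for blood pressure; the likely cost is a small loss of SBP precision, not bias

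*Protocol*

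**What the plan says.** Protocol Appendix D contains two arm rules.

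- **Patient factors, item 4** places the cuff on the patient's "nondominant arm. The proper sized cuff should fit snugly" and carries on with cuff fit. It names no visit and no exception.
- **Determination of the reference arm** has both arms measured at Visit 1 and then states: "The arm with the highest SBP will be determined at this visit". It adds that "BP should be measured always in this same arm throughout the study".
- **Measurement technique** follows the second rule. After an extra reading in the chosen arm at Visit 1, it says of all other on-site visits that "3 separate seated BPs should be measured in the selected arm with at least 1 minute between BP measurements".

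The body of the protocol adds no arm rule. Section 9.1.4.3 points to Section 9.2.1.5 and Appendix D, and Section 9.2.1.5 says "Full details and directions for the measurement of BP are presented in" Appendix D. SAP Section 2.1.4.5 analyses the mean of the three readings and does not mention the arm.

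These readings feed three things: the Week -1 SBP randomization stratum, the subset with Baseline SBP of at least 130 mmHg, and the tested Week 12 SBP endpoints. For 400 mg those endpoints are the subset and "Change from Baseline to Week 12 in SBP for all patients"; for 200 mg, the subset only.

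**The concern.** For a patient whose higher-SBP arm is the dominant arm, the two rules name different arms. A site could follow one rule at one visit and the other at the next. The inter-arm difference would then enter that patient's change score, and averaging three readings from the same arm would not remove it.

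A second route is the 130 mmHg cut. Even an arm used consistently, if it is the lower-reading one, shifts the level that decides the stratum and the subset.

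What is at stake is precision on SBP. Under Protocol Section 11.4.2.4 and SAP Section 2.4.4.4, SBP is tested at steps 4, 5 and 11 of a 13-step fixed sequence that stops at the first non-significant result. Failure at step 4 would leave 9 later comparisons untested, and failure at step 5 would leave 8. Protocol Section 11.1 bases power on HbA1c alone, so no stated margin for SBP shows how much extra noise these steps could absorb.

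**Working it through.** **Is the conflict real?** Both arms are measured at Visit 1, so item 4 has its main practical force at later visits. Those are the visits where the reference-arm paragraph says one arm is always to be used. No sentence limits item 4 to a visit or ranks the two rules. They agree when the higher-SBP arm is the nondominant one and conflict otherwise.

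**Plan's own figure.** There is none to reproduce. The only main-study power statements concern HbA1c and do not depend on the arm.

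**Inputs, all assumed because the documents give none:**
- SD of SBP change, s = 14 mmHg.
- Inter-arm SBP difference, D = 5 to 10 mmHg.
- Share of patients measured in different arms at Baseline and Week 12, q = 0 to 0.25.

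**Ceiling for q.** Suppose about half of patients are in conflict and the arm is chosen by coin-flip at each visit. A conflicted patient then has different arms with probability 2 × 0.5 × 0.5 = 0.5, so q = 0.5 × 0.5 = 0.25. If each site keeps to one rule, q = 0.

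**Added variance.** With switches equally likely in either direction, the variance ratio is (s² + qD²)/s²:

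| q | D (mmHg) | Ratio | Increase |
|---|---|---|---|
| 0 | any | 196/196 | 0% |
| 0.25 | 5 | (196 + 6.25)/196 = 1.032 | 3.2% |
| 0.25 | 10 | (196 + 25)/196 = 1.128 | 12.8% |

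If every switch goes the same way, the added variance is q(1 − q)D². At q = 0.25 that gives 4.69/196 = 2.4% for D = 5 and 18.75/196 = 9.6% for D = 10. There is also a mean shift, expected to be equal across the blinded groups.

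**Illustrative power for 400 mg versus placebo.** Two-sided 5% test, normal approximation: power = Φ(effect/SE − 1.96), with SE = SD × √(1/n₁ + 1/n₂). The effects of 4 and 5 mmHg and the subset size (half of each arm) are assumptions.

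| SD (mmHg) | All patients, 280 vs 140, 4 mmHg | Subset, 140 vs 70, 5 mmHg |
|---|---|---|
| 14.00 (no switching) | 78.8% | 68.4% |
| √202.25 = 14.22 | 77.6% | 67.1% |
| √221 = 14.87 | 73.9% | 63.2% |

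As an example, at SD 14.87 for all patients: SE = 14.87 × 0.1035 = 1.539, 4/1.539 = 2.60, and Φ(0.64) = 0.739.

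With a 10 mmHg between-group effect in the subset, power moves only from 99.8% to 99.6% at SD 14.87. Ten mmHg is the lower end of the Phase 2 reduction quoted in Protocol Section 4.5, which is not stated to be placebo-adjusted.

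These figures treat the endpoint as a simple change score. The planned ANCOVA adjusts for Baseline, so they indicate order of magnitude only.

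**The case against.** The strongest reply is that the governing rule is clear in context. The nondominant arm appears once, in a general list about reducing extraneous variation. The reference arm has its own headed paragraph and is then referred to twice more as the selected arm, for Visit 1 and for all other visits. A careful site would follow it, and a site that kept to either rule would add no inter-arm noise to the change score. This stands as a limit on the consequence. It does not remove the conflict: item 4 is an unqualified instruction, and item 5 prefers the cuff to be in place during the rest period, so staff working down the list meet item 4 first.

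A reader might infer more than the documents support:

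- **That the contradiction does add error to the SBP endpoints.** That requires the arm to differ within a patient between Baseline and Week 12. Nothing shows that this happens, and the text says to keep the same arm.
- **That the treatment comparison is biased.** Treatment is blinded, and the Week -1 and Baseline readings precede the first dose, so arm choice should not depend on group.
- **That variance could rise by a quarter.** A figure of 26% needs q = 0.5 with D = 10, since 50/196 = 0.26. If about half of patients are in conflict, every one of them would have to switch.
- **That the sequence is likely to break at the SBP steps.** Any source of noise could contribute to that, and no figure in the documents shows a material risk from this one.

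**Conclusion.** The wording conflict is certain, and it affects only patients whose higher-SBP arm is the dominant arm. Its size cannot be derived from the documents. Under the assumptions above, the variance of SBP change rises by between 0% and about 13%, and the upper end requires a coin-flip at each visit in every conflicted patient together with a 10 mmHg inter-arm difference. In the illustrations that worst case costs about 5 points of power when the assumed effect is 4 to 5 mmHg, and almost nothing when it is 10 mmHg. Some misclassification at 130 mmHg is also possible and is not quantified. This is a minor inconsistency in an operative measurement rule. It is worth correcting because the correction is nearly free, not because the SBP results are in doubt.

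**What to change.** In Appendix D, Patient factors item 4, replace the reference to the patient's nondominant arm with the reference arm selected at Visit 1. One rule then applies at every visit and matches the measurement-technique text. Send sites a short reminder. Appendix D already has all three readings entered in the eCRF; the form itself is not among the documents, so check whether it captures the arm and add a field if it does not. If Week 12 visits are already complete, ask sites which arm they used and report the answer as a limitation.

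The cost is one protocol edit, one site communication and possibly one eCRF field. No visit, endpoint or analysis changes.

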Appendix E General guidance for the follow-up of laboratory abnormalities by Sanofi

Neutropenia is to be recorded as an AE only if at least 1 of the criteria listed in the general guidelines for reporting AEs in [Section 10.4.2](#) is met.

[figure not shown]
THROMBOCYTOPENIA

Note:

The procedures above flowchart are to be discussed with the patient only in case described in the the event occurs. If applicable (according to local regulations), an additional consent (e.g., for HIV testing) will only be obtained in the case the event actually occurs.

Thrombocytopenia is to be recorded as an AE only if at least 1 of the criteria listed in the general guidelines for reporting AEs in [Section 10.4.2](#) is met.

[figure not shown]

*If unable to re-test in 72 hours, use original lab results to decide on further reporting/monitoring/discontinuation.

Note:

[figure not shown]
- “Baseline” refers to ALT sampled at Baseline Visit; or if Baseline value unavailable, to the latest ALT sampled before the Baseline Visit. The algorithm does not apply to the instances of increase in ALT during Screening.
- See [Section 10.4](#) for guidance on safety reporting.
- Normalization is defined as ≤ ULN or Baseline value, if Baseline value is >ULN.

ACUTE RENAL FAILURE

Acute renal failure is to be recorded as an AE only if at least 1 of the criteria listed in the general guidelines for reporting AEs in [Section 10.4.2](#) is met.

SUSPICION OF RHABDOMYOLYSIS

Suspicion of rhabdomyolysis is to be recorded as an AE only if at least 1 of the criteria in the general guidelines for reporting AEs in [Section 10.4.2](#) is met.

Appendix F Patient Qualitative Assessment of Treatment (PQAT)

Week 18 Assessment

The following questions ask for your opinion on the drug you received during this clinical study.

There are no right or wrong answers; we would like to better understand your own experience of the drug.

1. During this trial, so far, what were the main benefits you experienced with the drug you received?

2. During this trial, so far, what were the main disadvantages you experienced with the drug you received?

3. After this trial, would you be willing to continue using the drug you received during this trial?
Yes No

Please explain why?

4. Based on your own experience in this trial so far, please select a response on the scale below

The disadvantages of the drug I received significantly outweigh the benefits			There were equal benefits and disadvantages of the drug I received			The benefits of the drug I received significantly outweigh the disadvantages
 - 3	 - 2	 - 1	 0	 1	 2	 3

Week 52 Assessment

The following questions ask for your opinion **on the drug you received during this clinical study**.

There are no right or wrong answers; we would like to better understand your own experience of the drug.

- 1. In the past 6 months, what were the main benefits you experienced with the drug you received?**

- 2. In the past 6 months, what were the main disadvantages you experienced with the drug you received?**

- 3. After this trial, would you be willing to continue using the drug you received during this trial?**
Yes No

Please explain why?

- 4. Based on your own experience in the past 6 months, please select a response on the scale below**

The disadvantages of the drug I received significantly outweigh the benefits			There were equal benefits and disadvantages of the drug I received			The benefits of the drug I received significantly outweigh the disadvantages
 - 3	 - 2	 - 1	 0	 1	 2	 3

EFC14868 Amended Protocol 02

ELECTRONIC SIGNATURES

Signed by	Meaning of Signature	Server Date (dd-MMM-yyyy HH:mm)
██████████	Clinical Approval	10-Mar-2018 17:36 GMT+0100
██████████	Regulatory Approval	11-Mar-2018 17:30 GMT+0100
